## **15.0 Version History**

This Statistical Analysis Plan (SAP) for Study 3101-304-002 is based on the protocol amendment 2 dated 01 December 2020. Summary of changes from SAP version 1.0 to SAP version 2.0 is provided in [Table 10](#).

**Table 10. Summary of Changes from SAP Version 1.0 to SAP Version 2.0**

Date	Section	Description
08 JUL 2022	1.0	Add a description for tables specification in separate document
08 JUL 2022	1.0	Add a statement for changes to planned analysis in the protocol
15 JUL 2022	2.0	Modify the title of Section 2.0
05 JUL 2022	2.0	Add the objective of the study in Section 2.0
15 JUL 2022	2.3	Delete block sharing description
20 JUL 2022	2.3	Delete 'Asia/Pacific' from the whole document
12 JUL 2022	3.3	Update efficacy endpoints analyses of HIT-6 and MSQ 2.1 at Week 16
05 AUG 2022	4.0	Modify 'EU filing' to 'European submissions' in the whole document
30 JUL 2022	5.0	Update description of disposition summary
30 JUL 2022	5.0	Add a sub-group '< 4' to the factor 'number of migraine days during the screening/baseline period.'
30 JUL 2022	5.0	Delete disposition summary for mITT Population and Off-treatment Hypothetical Estimand Population
09 JUL 2022	5.0	Add comparing inconsistency between eDiary data and IWRS
09 JUL 2022	6.0	Update title for Section 6.0
05 AUG 2022	6.0	Provide the definition of participant-years
02 AUG 2022	7.1	Add Baseline efficacy parameters descriptions
29 JUL 2022	7.2	Modify Medical History summary table description
30 JUL 2022	7.2	Add a section for non-drug therapy
09 JUL 2022	7.3	Modify concomitant medications summary table description
30 JUL 2022	7.3	Add $\geq 5\%$ common concomitant medication summary table
01 AUG 2022	7.4	Move Protocol Deviations section from Appendix to Section 7.4
30 JUL 2022	8.0	Delete 'of primary endpoint'
07 JUL 2022	9.1	Add the definitions of migraine day, headache day and acute medication use day.
30 JUL 2022	9.3.2	Add 'mITT Population'
07 JUL 2022	9.3.3	Add a sentence to summarize sensitivity and supplementary analyses
30 JUL 2022	9.3.3	Clarify no missing data in ANCOVA model
01 AUG 2022	9.4	Modify the title of Section 9.4
30 JUL 2022	9.4.2	Clarify only providing descriptive statistics for MSQ 2.1 and HIT-6 data at Visit 8

Date	Section	Description
30 JUL 2022	9.4.2	Modify 'individual' to 'Participant'
10 JUL 2022	9.5	Add PHQ-9, HIT-6 and MSQ 2.1 in the summary description
30 JUL 2022	9.5	Add factor 'region' in the GLMM model
10 JUL 2022	9.5	Add a description for models not converged.
07 JUN 2022	9.6	Revise this section for additional subgroup and model specifications
10 JUL 2022	10.2	Add a section to describe AEs obtained in 3101-312-002 study
29 JUL 2022	10.2.1	Modify AE summary table description
10 JUL 2022	10.2.1	Indicate the population as 'participants who entered the safety follow-up period'
29 JUL 2022	10.2.2	Delete 'Any severe treatment emergent AE' and 'Any treatment emergent AE leading to death'
31 JUL 2022	10.2.3	Delete 'by participant number and SOC and PT'
28 JUL 2022	10.2.3	Add '[after rounding]'
31 JUL 2022	10.2.4	Revise this section for TESAEs and Deaths
31 JUL 2022	10.3	Delete the sentences for local lab and lab due to SAE.
01 AUG 2022	10.3	Add descriptions for AEs with PCS listings of Lab, vital sign and CSSRS data.
15 JUN 2022	10.3	Revise '>' to '≥' for Hy's Law definition
02 AUG 2022	10.4	Provide the definitions of Orthostatic vital signs parameters
08 JUL 2022	13.0	Remove '(P1)' and '(S1)'
08 AUG 2022	14.2	Add a summary for Covid-19 analyses
04 AUG 2022	15.0	Revise protocol version and SAP version history
05 AUG 2022	15.1	Add a section for 'Changes to Planned Analyses in the Protocol'
04 AUG 2022	Appendix A	Add Appendix A for List of SAP Signatories
04 AUG 2022	Appendix C	Update the definition of AESI
31 JUL 2022	Appendix D	Delete SI Units for 'Glucose' and 'Protein.' Update PCS of 'Glucose'
31 JUL 2022	Appendix E	Remove 'Triglycerides' from lab parameters
20 JUL 2022	Appendix F	Update the List of Abbreviations

**Table 11. SAP Version History Summary**

Version	Date	Summary
1.0	11 MAY 2021	Initial Version
2.0	21 AUG 2022	Final Version

### **15.1 Changes to Planned Analyses in the Protocol**

Collection and Derivation of Primary and Secondary Efficacy Assessments in protocol Section 9.4.1.1.4 was updated. Original "12 days" criteria for using prorated approach were modified to "14 days."

The subgroup analyses for the primary efficacy endpoint (protocol Section 9.4.4) were updated in SAP Section [9.6](#).

## **Appendix B. Derivation of Efficacy Variables**

### **A.1 Derivation of Efficacy Endpoints Based on eDiary Data**

For analysis purposes, four weeks (28 days) will be considered as one month. On a daily basis during the 4-week baseline period and throughout the double-blind treatment period, participants are to record eDiary information on the duration of headache, headache specific characteristics and symptoms, the pain severity, and use of any acute headache pain medication (see protocol Sections 8.1.1, 8.1.2, 8.1.3). Daily headache diary data consists of data from "today's diary" completed on that day and "yesterday's diary" completed on the following day. Participants are to report headache data in "today's diary" in the evening at any time from 19:00 to 23:59 and to complete "yesterday's diary" on the following day to add the remaining headache data of previous evening until midnight. In case participants miss "today's diary," they can report the whole-day headache data in "yesterday's diary" on the following day. In case participants miss "yesterday's diary," headache data from "today's diary" alone will be used as daily headache diary data. If both "today's diary" and "yesterday's diary" are missing on one day, the daily headache diary data will be treated as missing.

Daily headache diary data will be merged from "today's diary" and "yesterday's diary" as following and will be used to derive migraine day and headache day.

- Daily headache total duration: summation of headache durations from "today's diary" and "yesterday's diary"
- Daily headache pain severity: the worst pain severity from "today's diary" and "yesterday's diary"
- Daily headache characteristics and symptoms: present if present in one of "today's diary" and "yesterday's diary"
- Daily acute headache medication usage: combination of acute headache medications usage from "today's diary" and "yesterday's diary."
- For the derivation of headache day, the participant is considered to have taken a non-antiemetic acute headache medication if the participant has taken such a medication in either "today's diary" or "yesterday's diary."

Moderate/severe headache day is defined as a headache day during which the maximum pain severity is either moderate or severe. Severe headache day is defined as a headache day during which the maximum pain severity is severe.

If a participant confirmed no headache for the Question 1 in eDiary, then the participant will not answer subsequent questions related to headache symptoms, duration, and acute headache medication use by design. Thus, the acute medication use for that diary ('today' or 'yesterday') will be treated as 'No' when deriving acute medication use day.

The monthly migraine days is defined the total number of recorded migraine days in the eDiary divided by the total number of days with eDiary records during each monthly period and multiplied by 28. For baseline, a minimum of 20 days' eDiary data during the 4-week baseline period is required for the migraine days to be evaluable. For each postbaseline 4-week treatment period, a minimum of 14 days' eDiary data during that period is required for the migraine days to be evaluable. If a participant does not have at least 14 days of diary data for a monthly treatment period, the migraine days for that period will be considered as missing. Migraine days will be derived for each participant at baseline and for each postbaseline monthly treatment period (Weeks 1-4, 5-8, 9-12). The same method to derive monthly migraine days will be used to derive monthly headache days, monthly acute medication use days, monthly triptan use days, monthly cumulative headache hours, monthly moderate/severe headache days, and monthly severe headache days.

If a participant confirmed that acute medications were taken and entered medications in the eDiary, then the acute medication use day will be set to 'Yes.' If a subject reports 'Yes' to the intake of allowed medication(s) to treat an acute migraine but does not list any of them in the diary, then the acute medication use days will not be counted in this situation and vice versa.

## A.2 Derivation of Health Outcome Endpoints

### AIM-D Related Endpoints Derivation

The AIM-D was developed as a daily eDiary with a recall period 24 hours. By design, it is collected in the today diary only. The scoring of the following endpoints is completed in 2 steps.

- Monthly Performance of Daily Activities domain score of the AIM-D
- Monthly Physical Impairment domain score of the AIM -D
- Monthly AIM -D total score

Step 1: Calculate AIM-D daily domain score and total score

Daily performance of daily activities score will be calculated based on the summation of items 1-5 and 10 and 11, ranging from 0-35. A daily performance of daily activities domain score will be calculated if 4 or more item scores have non-missing responses. When the response category "I did not have <errands, leisure or social, strenuous activities> planned" (items 2, 4, and 5), is selected, the response will be considered missing. The corresponding performance of daily activities domain score will be calculated by summing the non-missing item scores and dividing by the number of non-missing items and then multiplying by 7, provided that 4 or more item scores are available; otherwise, it will be set to missing. The raw daily score will be transformed to a 0-100 scale by multiplying by 100 and dividing by the highest raw score (35).

Daily physical impairment scores will be calculated based on the summation of items 6-9, ranging from 0-20. A daily physical Impairment score will be calculated if 2 or more item scores have non-missing responses. The corresponding physical Impairment score will be calculated by summing the non-missing item scores and dividing by the number of non-missing items and then multiplying by 4, provided that 2 or more item scores are available; otherwise, it will be set to missing. The raw daily score will be transformed to a 0-100 scale by multiplying by 100 and dividing by the highest raw score (20).

A daily total score will be calculated based on the summation of items 1-11, ranging from 0-55. A Total Score will be calculated if 6 or more items scores have non-missing responses. When the response category "I did not have <errands, leisure or social, strenuous activities> planned" (items 2, 4, and 5), is selected, the response will be considered missing. The corresponding Total Score will be calculated by summing the non-missing item scores and dividing by the number of non-missing items and then multiplying by 11, provided that 6 or more item scores are available; otherwise, it will be set to missing. The raw score will be transformed to a 0-100 scale by multiplying by 100 and dividing by the highest raw score (55).

#### Step 2: Calculate Monthly Scores and Baseline Score

Monthly scores will be calculated using the average daily scores only if there are at least 14 non-missing daily scores in the corresponding monthly (28-day) period. The corresponding monthly scores will be calculated by summing the non-missing daily domain scores and dividing by the number of non-missing daily domain, provided that 14 or more daily scores are available; otherwise, it will be set to missing.

#### Activity Level and Activity Limitation

Monthly activity level score will be calculated by summing the non-missing daily scores and dividing by the number of these scores, provided that 14 or more daily scores are available in the corresponding monthly (28-day) period; otherwise, it will be set to missing. Same rule will be applied to the calculation of monthly activity limitation score.

#### MSQ Related Endpoints Derivation

MSQ v2.1 consists of 14 items with a 4-week recall period. The scoring of the MSQ is completed in following 3 steps.

Step 1: Final item value assignment.

Precoded item values and final item values for each MSQ item response are shown in [Table 12](#).

**Table 12. Item Values for MSQ Item Responses**

Response Categories	Precoded Item Value	Final Item Value
None of the time	1	6
A little bit of the time	2	5
Some of the time	3	4
A good bit of the time	4	3
Most of the time	5	2
All of the time	6	1

Step 2: Computation of raw domain (dimension) scores

Once a final item value has been assigned to each item, a raw score can be computed for each MSQ domain. Role Function Restrictive domain includes Items 1 - 7, Role Function Preventive domain includes Items 8 - 11, and Emotional Function domain includes Items 12 - 14. The raw score for each domain is the algebraic sum of the final item values for all items in that domain.

Missing data handling: if a respondent answered at least half of the items in a domain (or half plus one in the case of scales with an odd number of items), a missing item value can be estimated using the average of the other completed items within the same dimension.

In detail, for MSQ v2.1 Role Function Restrictive domain, the 7 individual item responses using final item value will be summed, resulting in the raw domain score ranging from 7 to 42 with higher scores indicating better quality of life. If there are missing item responses, the raw domain score will be calculated by summing the non-missing item responses using final item value and dividing by the number of non-missing items and

then multiplying by 7 provided that 4 or more items in the domain are completed; otherwise it will be set to missing. For MSQ v2.1 Role Function Preventive and Emotional domains, the raw domain scores will be calculated similarly using final item value respectively. If there are missing item responses, the corresponding raw domain score will be calculated by summing the non-missing item responses using final item value and dividing by the number of non-missing items and then multiplying by the number of questions in that domain provided that 2 or more domain items are completed; otherwise it will be set to missing.

Step 3: Linear transformation to a 0 to 100 scale.

The transformation formula for each MSQ 2.1 domain is listed below

- Role Function -Restrictive:
- Role Function-Preventive:
- Emotional Function:

#### HIT-6 Total Score Derivation

For HIT-6 total score, pre-coded item values and final item values for each item response are shown in [Table 13](#). Total score is calculated by summing 6 sub-item responses, resulting in the total score ranging from 36 to 78 with higher scores indicating greater impact. If any sub item is missing, then total score will be missing.

**Table 13. Item Values for HIT-6 Item Responses**

Response Categories	Precoded Item Value	Final Item Value
Never	0	6
Rarely	1	8
Sometimes	2	10
Very Often	3	11
Always	4	13

The HIT-6 instrument has a recall period of 4 weeks for 3 of the 6 items.

#### MIDAS Related Endpoints Derivation

MIDAS total score is derived as the sum of first 5 of questions (i.e., the sum of days missing work or school, Productivity at work or school reduced, Not do household work, Productivity in household work reduced, Miss family social or leisure activities). If any sub item is missing, the MIDAS total score will be missing.

The MIDAS absenteeism score is derived as the sum of Questions 1, 3 and 5. If any sub item is missing, then the MIDAS absenteeism score will be missing. The MIDAS presenteeism score is derived as the sum of Questions 2 and 4. If any sub item is missing, then the MIDAS presenteeism score will be missing.

#### WPAI: MIGRAINE Related Endpoints Derivation

WPAI outcomes are expressed as impairment percentages, with higher numbers indicating greater impairment and less productivity, i.e., worse outcomes, as follows:

Questions:

- Q1 = currently employed (working for pay).
- Q2 = missed work hours because of problems associated with your migraine
- Q3 = missed work hours due to other reason.
- Q4 = hours actually worked.
- Q5 = migraine affected productivity while working.
- Q6 = migraine affected regular daily activity.

Scores:

Multiply scores by 100 to express in percentages.

- Percent work time missed due to migraine (absenteeism):  $Q2/(Q2 + Q4)$

- Percent impairment while working due to migraine (presenteeism): Q5/10
- Percent overall work impairment due to migraine (overall work productivity loss):  $Q2/(Q2 + Q4) + (1 - (Q2/(Q2 + Q4))) \times (Q5/10)$
- Percent activity impairment due to migraine (regular activity impairment): Q6/10

If the response to Q1 ("Currently employed?") is No or missing, absenteeism, presenteeism, and overall work productivity loss will all be set to missing.

#### EQ-5D-5L Score Derivation

The EQ-5D-5L is made up of two components: health state description and evaluation. The description component consists of five dimensions: mobility, self-care, usual activities, pain/discomfort, and anxiety/depression. The mobility dimension queries the participant's walking ability. The self-care dimension queries the participant's ability to wash or dress by himself. The usual activities dimension assesses the participant's performance in "work, study, housework, family or leisure activities." The pain/discomfort dimension measures how much pain or discomfort a participant has. The anxiety/depression dimension assesses how anxious or depressed a participant is. The respondents rate their level of severity for each dimension using a 5-level scale (EQ-5D-5L) by ticking (or placing a cross) in the box against the most appropriate statement in each of the 5 dimensions. The second component of the EQ-5D-5L is a visual analogue scale (EQ-VAS) by which participants can rate their overall health from 0 (worst imaginable health state) to 100 (best imaginable health state).

With the EQ-5D-5L, rating levels can be coded as numbers 1, 2, 3, 4 or 5 which correspond to "have no problems," "have slight problems," "have moderate problems," "have severe problems," and "unable to do/have extreme problems," respectively. As a result, a participant's health state can be defined by a 5-digit number by combining the numeric levels from the 5 dimensions, ranging from 11111 ("have no problems" in all 5 dimensions) to 55555 ("unable to do/have extreme problems" in all 5 dimensions). The

index value for the EQ-5D-5L will be derived using an international standardized protocol.

EQ-5D-5L will be captured on eDiary during 7 days in the screening/baseline period and during specific time periods for Visit 1 to 7, except at Visit 8 (Week 16) where it will be administered on an eTablet. The index score and VAS score for a specific period will be calculated as the average of available scores in that period respectively if at least 50% of daily scores are available; otherwise, the scores will be set as missing. For example, for a period of 14 days, at least 7 assessments are required; and for a period of 7 days, at least 4 assessments are required.

#### PROMIS-PI T-Score Derivation

The PROMIS-PI measures self-reported interference of pain on relevant aspects of daily life (i.e., social, cognitive, emotional, physical, recreational) over the past 7 days. A 5-level response scale for all 6 items ranges from 1 to 5, corresponding to item response of "Not at all" to "Very much." The raw score of PROMIS-PI is the sum of all 6 items, ranging from 6 to 30. If one or more items are missing, the raw score will be set to missing. A raw score can be standardized into a T-score with a mean of 50 and standard deviation of 10 using [Table 14](#). Higher raw or T-scores indicate greater pain interference.

**Table 14. PROMIS-PI Raw Score Transformation**

Raw Score	T-Score	Raw Score	T-Score	Raw Score	T-Score	Raw Score	T-Score
6	41.1	13	56.6	20	63.0	27	69.8
7	48.6	14	57.6	21	63.8	28	71.0
8	50.7	15	58.6	22	64.8	29	72.6
9	52.2	16	59.5	23	65.7	30	76.3
10	53.4	17	60.4	24	66.7		
11	54.5	18	61.2	25	67.6		
12	55.6	19	62.1	26	68.7		

Patient Health Questionnaire (PHQ-9)

The PHQ-9 consists of the 9 diagnostic criteria for depressive disorders in the past 2 weeks from the DSM-IV. Participants are asked to indicate the frequency with which they have been bothered by 9 symptoms of depressive disorders over the previous 2 weeks, on a 4-point scale: 0 (not at all), 1 (several days), 2 (more than half the days), and 3 (nearly every day). The total score ranges from 0 to 27 (from best to worst). A score of 15 to 19 is considered as moderately severe depression and 20 to 27 as severe depression. A Total Score will be calculated using  $(\text{sum of non-missing items}) \times 9 / (\text{number of non-missing items})$  if 5 or more items scores have non-missing responses.

## **Appendix C. Definition of Adverse Events of Special Interest**

The definition of Adverse Events of Special Interest (AESI) is described in Section [10.2.5](#)

## Appendix D. Potentially Clinically Significant Criteria for Safety

The potentially clinically significant criteria for clinical laboratory parameters, vital signs and ECG parameters are provided in the following tables.

Clinical laboratory parameters are provided in the following tables.

**Table 15. Potentially Clinically Significant Criteria for Clinical Laboratory Parameters**

Category	Parameter	SI Unit	PCS Criteria	
			PCS Low	PCS High
Chemistry	Albumin	g/L	$< 0.8 \times \text{LLN}$	$> 1.2 \times \text{ULN}$
	Alanine aminotransferase	U/L	—	$\geq 3.0 \times \text{ULN}$
	Alkaline phosphatase	U/L	—	$\geq 3.0 \times \text{ULN}$
	Aspartate aminotransferase	U/L	—	$\geq 3.0 \times \text{ULN}$
	Bicarbonate	mmol/L	$< 0.9 \times \text{LLN}$	$> 1.1 \times \text{ULN}$
	Bilirubin, total	$\mu\text{mol/L}$	—	$\geq 1.5 \times \text{ULN}$
	Blood urea nitrogen	mmol/L	—	$> 1.5 \times \text{ULN}$
	Calcium	mmol/L	$< 0.9 \times \text{LLN}$	$> 1.1 \times \text{ULN}$
	Chloride	mmol/L	$< 0.9 \times \text{LLN}$	$> 1.1 \times \text{ULN}$
	Cholesterol, total	mmol/L	—	$> 1.6 \times \text{ULN}$
	Creatinine	$\mu\text{mol/L}$	—	$> 1.5 \times \text{ULN}$
	Creatine kinase	U/L	—	$> 2.0 \times \text{ULN}$
	Estimated glomerular filtration rate	$\text{mL/min}/1.73\text{m}^2$	$< 60$ $\text{mL/min}/1.73\text{m}^2$	—
	Glucose, nonfasting	mmol/L	$< 0.8 \times \text{LLN}$	$> 2.0 \times \text{ULN}$
	Lactate dehydrogenase (LDH)	U/L	—	$> 3.0 \times \text{ULN}$
	Phosphorus	mmol/L	$< 0.9 \times \text{LLN}$	$> 1.1 \times \text{ULN}$
	Potassium	mmol/L	$< 0.9 \times \text{LLN}$	$> 1.1 \times \text{ULN}$
	Protein, total	g/L	$< 0.9 \times \text{LLN}$	$> 1.1 \times \text{ULN}$
	Sodium	mmol/L	$< 0.9 \times \text{LLN}$	$> 1.1 \times \text{ULN}$
	Uric acid	$\mu\text{mol/L}$	—	$> 1.2 \times \text{ULN}$

Category	Parameter	SI Unit	PCS Criteria	
			PCS Low	PCS High
Hematology	Basophils, absolute cell count	10  /L	—	> 2.0 × ULN
	Eosinophils, absolute cell count	10  /L	—	> 2.0 × ULN
	Hematocrit	Ratio	< 0.9 × LLN	> 1.1 × ULN
	Hemoglobin	g/L	< 0.9 × LLN	> 1.1 × ULN
	Lymphocytes, absolute cell count	10  /L	< 0.7 × LLN	> 1.3 × ULN
	Monocytes, absolute cell count	10  /L	< 0.5 × LLN	> 2.0 × ULN
	Neutrophils, absolute cell count	10  /L	< 0.7 × LLN	> 1.3 × ULN
	Platelet count	10  /L	< 0.5 × LLN	> 1.5 × ULN
	Red blood cell count	10  /L	< 0.9 × LLN	> 1.1 × ULN
	White blood cell count	10  /L	< 0.9 × LLN	> 1.5 × ULN
Urinalysis	pH	pH	< 0.9 × LLN	> 1.1 × ULN
	Glucose	—	—	Positive 
	Protein	—	—	Positive 
	Specific gravity	—	—	> 1.1 × ULN

LLN = lower limit of normal value; ULN = upper limit of normal value; normal value provided by laboratory.

SI = Le Système International d'Unités (International System of Units).

1. Any results other than trace or normal will be considered as positive.
2. Any results other than trace or negative will be considered as positive.

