8.2.4. Clinical Safety Laboratory Assessments

See Section 10.2 (Appendix 2) for the list of clinical laboratory tests to be performed and the SoA for the timing and frequency. Hematology, chemistry, coagulation parameters (INR), and urinalysis will be conducted at each visit. Serology and the urine drug screen will be conducted at Screening (Visit 1). Investigators may also perform unscheduled clinical laboratory determinations at any time for the purpose of participant safety. Participants are not required to fast overnight before coming in for their appointments.

At screening, the investigator or subinvestigator will assess the clinical significance of any values outside the reference ranges provided by the laboratory, and participants with abnormalities judged to be clinically significant will be excluded from the study.

The investigator must review the laboratory report, document this review, and record any clinically relevant changes occurring during the study in the AE section of the eCRF. The laboratory reports must be filed with the source documents. Clinically significant abnormal laboratory findings are those that are not associated with the underlying disease, unless judged by the investigator to be more severe than expected for the participant's condition.

Positive results with the urine drug screen at Visit 1, unless explained by previously reported concomitant medication use, will be excluded from the study. Urine drug screens positive for recreational (including cannabis regardless of legality) or illicit drugs or non-disclosed concomitant medications are not allowed to be repeated. All other positive urine drug screens may only be repeated with permission from the Sponsor.

A positive pregnancy test at Visit 1 or Visit 2 will exclude the participant from participation in the study. Participants who are confirmed to be pregnant during the study will be withdrawn.

All laboratory tests with values considered clinically significant during participation in the study or within 30 days after the last dose of study intervention should be repeated until the values return to normal or baseline or are no longer considered clinically significant by the investigator.

If such values do not return to normal/baseline within a period of time judged reasonable by the investigator, the etiology should be identified and the sponsor notified.

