10.2. Appendix 2: Clinical Laboratory Tests

The tests detailed in [Table 10-1](#) below will be performed by the central laboratory. Blood and urine samples will be collected, processed, and stored according to the instructions provided by the laboratory.

Protocol-specific requirements for inclusion or exclusion of participants are detailed in [Section 5](#) of the protocol.

Additional tests may be performed at any time during the study as determined necessary by the investigator or required by local regulations.

Participants are not required to fast overnight before coming in for their appointments.

Investigators must document their review of each laboratory safety report.

Table 10-1 Protocol-required Laboratory Assessments

Category	Parameter
Chemistry	Sodium, potassium, chloride, bicarbonate, glucose, blood urea nitrogen, creatinine, total bilirubin, alkaline phosphatase, AST, ALT, lactate dehydrogenase, creatine kinase, total protein, serum albumin, calcium, phosphorus, uric acid, total cholesterol. The estimated glomerular filtration rate will be calculated by the central laboratory.

Hematology	Hemoglobin; hematocrit; red blood cell count; red blood cell indices (mean corpuscular volume, mean corpuscular hemoglobin, mean corpuscular hemoglobin concentration); white blood cell count, including differential (neutrophils, lymphocytes, monocytes, eosinophils, and basophils); platelet count
Urinalysis	Urine dipstick for specific gravity, pH, protein, glucose, ketones, bilirubin, and blood; microscopic exam including red blood cells/high-power field, white blood cells/high-power field, and casts/low-power field.
Coagulation	International normalized ratio
Serology	At Visit 1 only: anti-hepatitis A IgM antibody, hepatitis B surface antigen, anti-hepatitis C antibody, anti-hepatitis E IgM antibody
Urine Drug Screen	Screening for drugs of abuse (eg, marijuana, cocaine, phencyclidine, amphetamines, benzodiazepines, barbiturates, opiates) will be conducted using a urine drug screen at Visit 1. Urine drug screens positive for recreational (including cannabis regardless of legality) or illicit drugs or non-disclosed concomitant medications are not allowed to be repeated. All other positive urine drug screens may only be repeated with permission from the Sponsor. A negative result or an explanation of a positive result due to concomitant medication use (eg, benzodiazepines for insomnia) will be required for randomization.

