### 10.3 Laboratory Data

The clinical laboratory tests defined in the protocol (e.g., hematology, clinical chemistry and urinalysis) will be summarized.

Each laboratory variable will be summarized for all time points (starting with Baseline) with the number of non-missing observations, mean and standard deviation, median, Q1, Q3, minimum and maximum. Mean change from baseline to each applicable post-baseline visit will be summarized with the number of observations, baseline mean, and visit mean. The change from baseline mean, standard error will be presented for the mean change from baseline within each treatment group. In addition, descriptive statistics for values and changes from the baseline values in conventional units at each assessment time point will be presented for selected clinical laboratory parameters listed in [Appendix E](#). A description of reporting the lab values in conventional units in patient narratives (along with the standard reporting in SI units) is presented at the end of [Appendix E](#).

Changes in laboratory parameters will be tabulated using shift tables categorized as low, normal, or high based on the normal ranges of the laboratory used for each sample. A shift table will be provided to summarize shifts from baseline to the final post-baseline value.

Laboratory abnormalities will be evaluated based on potentially clinically significant (PCS) criteria ([Table 15](#)). For each laboratory PCS criterion, the number and percentage

of participants who have a laboratory value meeting the criteria will be summarized. Listings will be provided to summarize subject-level laboratory data for participants meeting PCS criteria. A listing of all AEs for participants with PCS Lab values will be provided.

In addition, ALT, AST, alkaline phosphatase, and total bilirubin will be categorized in [Table 16](#). The number and percentage of participants meeting each of the criteria for postbaseline hepatic laboratory abnormalities listed in [Table 16](#) will be summarized. The percentages will be calculated relative to the number of participants with at least 1 available postbaseline assessment. The numerator will be the total number of participants having at least 1 postbaseline value that meets the specific category during the study. A supportive listing will also be provided.

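### The urine specific gravity flag in SAP Table 15 (more than 1.1 times ULN) cannot fire unless the dipstick reports values above 1.100, so its row in the safety tables is probably empty by construction

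*SAP*

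**What the plan says.** SAP Appendix D, Table 15 lists the urinalysis entry as "Specific gravity — — > 1.1 × ULN". There is no low criterion and no unit. The footnote defines the limit only by its source: "ULN = upper limit of normal value; normal value provided by laboratory". Neither document gives a numerical ULN for specific gravity.

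Protocol Section 10.2, Table 10-1 sets the method: "Urine dipstick for specific gravity, pH, protein, glucose, ketones, bilirubin, and blood". The reading range of the strip is not stated. Protocol Section 8.2.4 sets the frequency: "Hematology, chemistry, coagulation parameters (INR), and urinalysis will be conducted at each visit".

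SAP Section 10.3 says how the criterion is used: for each one, "the number and percentage of participants who have a laboratory value meeting the criteria will be summarized". Participants who meet a PCS criterion are also listed, and a further listing shows all AEs of participants with PCS laboratory values. No other part of either document gives a different rule for specific gravity. In the same block of Table 15, urine glucose and protein, also dipstick tests, are flagged when positive and not by a multiple of a limit.

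**The concern.** A multiplier of 1.1 on the ULN suits a quantity whose scale starts at zero, such as hemoglobin, because a value 10% above the limit then means 10% more of the substance measured. Specific gravity does not work that way. Plain water reads 1.000, and all the information lies in the excess above it. Multiplying the whole reading by 1.1 adds at least 0.100, several times the span from water to any plausible upper limit.

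Since the table has no low criterion, this is the row's only route to a flag. If the cutoff lies beyond what the strip reports, the table prints zero in each arm regardless of the data. A reader of the study report would have no way to tell that zero from an observed absence of markedly high values.

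**Working it through.** **Inputs**

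- Criterion: more than 1.1 × ULN (SAP Table 15).
- ULN: supplied by the laboratory and not printed. Assumed here to be 1.025 to 1.040.
- Top reading of the dipstick (R): not printed. Varied here from 1.030 to 1.100.
- Reference point: water = 1.000, from the definition of specific gravity.

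The plan states no numerical cutoff, so there is no figure of its own to reproduce.

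**Step 1. The cutoff and its distance from water**

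Cutoff = 1.1 × ULN. Multiple of the excess at ULN = (1.1 × ULN − 1) / (ULN − 1).

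| Assumed ULN | Cutoff | Excess at cutoff / excess at ULN | Multiple |
|---|---|---|---|
| 1.025 | 1.1275 (1.128) | 0.1275 / 0.025 | 5.1 |
| 1.030 | 1.133 | 0.133 / 0.030 | 4.4 |
| 1.035 | 1.1385 (1.139) | 0.1385 / 0.035 | 4.0 |
| 1.040 | 1.144 | 0.144 / 0.040 | 3.6 |

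**Step 2. Does the result depend on the assumed ULN?**

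The lowest cutoff arises at the lowest conceivable limit, ULN = 1.000: 1.1 × 1.000 = 1.100. Any higher ULN moves the cutoff further up. The bound of 1.100 therefore needs no assumption beyond a ULN that is not below water.

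**Step 3. The inverse check**

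For a strip whose top reading is R, the flag can fire only if R > 1.1 × ULN, that is, if ULN < R / 1.1.

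| Assumed top reading R | ULN would have to be below |
|---|---|
| 1.030 | 0.936 |
| 1.040 | 0.945 |
| 1.060 | 0.964 |
| 1.080 | 0.982 |
| 1.100 | 1.000 |

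Every strip topping out at or below 1.100 would need an upper limit of normal below that of water. The one open input is whether the strip reports above 1.100.

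**The case against.** The strongest objection is to overstatement. A reader might infer that the row can never flag anyone, or that the expected count is 0 of about 300. The documents do not support either as a flat statement. Both depend on the top reading of the dipstick, which neither the protocol nor the SAP gives. What the documents support is conditional: the flag cannot fire unless the strip reports above 1.100. Likewise, a cutoff of about 1.13 to 1.14 holds only for a ULN of about 1.027 to 1.036 (1.13 / 1.1 and 1.14 / 1.1); the firm statement is at least 1.100.

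A reader might also call this a calculation error in the SAP. It is not, because the SAP states no figure that fails to reproduce. The threshold is simply unsuited to the scale.

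The second objection is that other outputs cover much of the gap. SAP Section 10.3 summarizes every laboratory variable at each time point, including the maximum, and gives a low/normal/high shift table against the laboratory's range. Protocol Section 8.2.4 has the investigator review each laboratory report and record clinically relevant changes as AEs. A PCS value is also meant to be a stricter category than an abnormal one, so a zero in this row need not be read as no abnormal values. Most of this stands, and it keeps the point small. It does not rescue the row. The shift table compares baseline with the final post-baseline value only, so a high value at an intermediate visit shows up in the visit-level summaries or listings but not in a participant count. The PCS row is the place for that count.

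**Conclusion.** The point holds in conditional form. For any ULN of 1.000 or more the cutoff is at least 1.100, and for assumed ULNs of 1.025 to 1.040 it is 1.128 to 1.144. If the dipstick does not report above 1.100, the specific gravity row is zero in both arms by construction and tells the reader nothing. The conclusion is insensitive to the unprinted ULN and rests on one fact that the sponsor can look up, the strip's reported range.

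The consequence is minor: one descriptive urinalysis row and its listings. Efficacy, type I error, adverse events of special interest and the hepatic analyses are unaffected.

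**What to change.** Confirm the reported range of the strip from the laboratory manual, then change the one cell in Table 15 in one of two ways.

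- Replace the multiplier with a criterion on the scale that the assay reports, such as above ULN. The cost is more participants in the PCS listing and in the associated AE listing, and overlap with the high category of the shift table. How many more cannot be estimated from the documents. This option is useful only if the reported scale extends past the laboratory's ULN, which the same check settles.
- Delete the row and report specific gravity through the descriptive statistics and the shift table. This does not depend on the strip's range. The cost is that no any-visit participant count is given for specific gravity.

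Either is a one-cell edit with a small programming change.
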